13.6.6 Assessment of Outcome

Event outcome at resolution or time of last follow-up will be recorded as: recovered, recovering, not recovered, recovered with sequelae, fatal, or unknown.

13.7 Adverse Event Reporting Procedures

13.7.1 All Adverse Events

Any clinically significant AE that is ongoing at the time of study completion or ET will be followed by the Investigator until event resolution, the AE is otherwise explained, the AE is not considered clinically significant by the Investigator, or the patient is lost to follow-up.

All non-serious AE identified will be recorded in the Adverse Event eCRF beginning from the time of first study drug infusion and ending on Extension Day 561 (± 3) or 84 (± 3) days after last dose of study drug if ET. All SAE identified will be recorded in the Adverse Event eCRF beginning from the time of first study drug infusion and ending on Extension Day 561 (± 3) or 84 (± 3) days after last dose of study drug if ET. Whenever appropriate, the CTCAE (version 5.0 or most current version) should be used for naming common AE ([Appendix 3](#)).

13.7.2 Serious Adverse Event Reporting

In the event of any SAE reported or observed during the study, whether or not attributable to the study drug, site personnel must report it immediately (**within 24 hours of becoming aware of the SAE**) by telephone, fax, or email to the Sponsor, Allakos Inc.

The SAE report forms will be provided to the investigational site to assist in collecting, organizing, and reporting SAE, and the forms must be completed with as much information as is available and should be submitted to the Sponsor within 24 hours of becoming aware of the event. Serious adverse events must also be recorded on the Adverse Event eCRF and designated as “serious.”

Even when only minimal information is available for the initial SAE report, the Investigator should try to make a causality assessment, as the causality is used to determine the timing of regulatory reporting requirements. If the Investigator or designee is not available to sign the SAE report on initial submission, they should be contacted by telephone and their assessment documented on the SAE report form (with a note stating that signature is forthcoming). The Investigator *may change* their causality assessment based on follow-up information and submit an amended SAE report form.

All efforts will be made to obtain accurate and complete medical records for the SAE. All efforts to obtain information should be documented in the patient source documents.

The site will notify the Institutional Review Board (IRB) according to its guidelines.

The patient's condition will be followed by the Investigator or designee until resolution of the condition or a return to baseline levels. If additional visits are required, the patient will be asked to return to the study site for further follow-up. If the condition is still ongoing at the time the patient exits the study, every effort will be made to continue to follow up with the patient for a reasonable period of time, as determined by the Investigator or until there is a return to baseline or stabilization of the condition. As additional information becomes available, such as hospital discharge notes and patient medical records, the Investigator will be notified and provided with all relevant information.

All SAE that have not resolved by the end of the study or that have not resolved on discontinuation of the patient's participation in the study must be followed until any of the following occurs:

- The event resolves.
- The event stabilizes.
- The event returns to baseline if a baseline value is available.
- The event can be attributed to agents other than the investigational product or to factors unrelated to study conduct.
- It becomes unlikely that any additional information can be obtained (patient or health care practitioner refusal to provide additional information, lost to follow-up after demonstration of due diligence with follow-up efforts).

Serious adverse events must be reported within 24 hours to:

SAE Reporting

[contact]

Email: [contact]

13.7.3 Pregnancy Reporting

Pregnancies are captured if they occur in female patients or in the sexual partners of male patients from the time the patient is first exposed to the investigational product through Extension Day 561 (± 3) or 84 (± 3) days after last dose of study drug if ET.

Female patients must be instructed to discontinue all study drugs and inform the Investigator immediately if they become pregnant during the study. Male patients must be instructed to inform the Investigator immediately if their partner becomes pregnant during the study.

The Investigator must report any pregnancy to Allakos within 24 hours of becoming aware of it using the provided pregnancy reporting forms. The patient must be immediately discontinued from study drug. An uncomplicated pregnancy will not be considered an AE or SAE, but all pregnancies in patients who received AK002 will be followed through term. For male patients with female partners who become pregnant, the site will ask the father (the study patient) to provide information about the outcome of the pregnancy and information about the baby. If detailed health information about the mother is requested by Allakos, a Pregnant Partner Information Release Form will be provided to the site for the mother to sign.

Any congenital abnormalities noted at birth in the offspring of a patient who received study drug will be reported as a SAE. The outcome of any pregnancy and the presence or absence of any congenital abnormality will be recorded in the source documentation and reported to the Medical Monitor and Sponsor.

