7.3 Inclusion Criteria

Patients are eligible for the study if all of the following criteria are met:

- 1) Provide written informed consent.
- 2) Completed Study AK002-016, defined as having received 6 infusions of study drug and followed through at least Day 176 (± 3) or completed Study AK002-012, defined as having received the cohort-appropriate number of doses and followed for 5 months after last dose of study drug.
- 3) If patient is on preexisting dietary restrictions, willingness to maintain those restrictions, until the seventh dose has been received. After the seventh dose, diet may be liberalized.
- 4) Able and willing to comply with all study procedures.

- 5) Female patients must be either postmenopausal for at least 1 year or surgically sterile (tubal ligation, hysterectomy, or bilateral oophorectomy) for at least 3 months, or if of childbearing potential, have a negative pregnancy test and agree to use dual methods of contraception or abstain from sexual activity until the end of the study or for 120 days following the last dose of study drug, whichever is longer.
- 6) Male patients with female partners of childbearing potential must agree to use a highly effective method of contraception (vasectomy is acceptable) until the end of the study or for 120 days following the last dose of study drug, whichever is longer. All fertile men with female partners of childbearing potential should be instructed to contact the Investigator immediately if they suspect their partner might be pregnant at any time during study participation.

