7.4 Exclusion Criteria

Patients will be excluded from the study if they meet any of the following criteria:

- 1) Poor tolerance to previous administration of AK002 in the opinion of the Investigator.
- 2) Known hypersensitivity to any constituent of the study drug.
- 3) Any disease, condition (medical or surgical), or cardiac abnormality, which, in the opinion of the Investigator, would place the patient at increased risk.
- 4) Planned or expected vaccination with live attenuated vaccines during the treatment period, or vaccination expected within 5 half-lives (4 months) of AK002 administration. All types and formulations of vaccines (including live attenuated vaccines) authorized by FDA or other regulatory authority for the prevention of COVID-19 may be administered before, during, or after this study. The vaccine should not be administered within 7 days prior to and within 7 days after the administration of AK002 so that any side effects caused by either of the 2 medications can be more easily determined.
- 5) Women who are pregnant, breastfeeding, or planning to become pregnant while participating in the study.
- 6) Any other reason that, in the opinion of the Investigator or Medical Monitor, makes the patient unsuitable for enrollment.

8. Concurrent Medications

Prior and concomitant medications include both prescribed and over-the-counter medications and will be recorded in the electronic Case Report Forms (eCRF). Medications taken for EG/EoD or symptoms of EG/EoD, as well as any medications taken within 30 days prior to extension study Day 1 should be recorded.

Medications taken prior to the study should be maintained, as much as possible. Patients should be advised against taking any new medication or stopping an existing medication, both prescribed and over-the-counter, without consulting the Investigator, unless the change is required for emergency use. Immediately prior to the first infusion, the study site personnel should ensure that the patient continues to meet the inclusion criteria and none of the exclusion criteria (including use of prohibited medications as per AK002-016 criteria).

All medications used during the conduct of the study must be documented.

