13.2 Serious Adverse Events

A SAE is defined as an AE that meets 1 of the following criteria:

- Death
- A life-threatening adverse event that places the patient at risk of death at the time of the event. It does not refer to an event that hypothetically might cause death if it were more severe.
- Inpatient hospitalization or prolongation of existing hospitalization.
- A persistent or significant disability/incapacity.
- A congenital anomaly/birth defect occurring in the offspring of a study patient.
- Other important medical events may also be considered a SAE when, based on appropriate medical judgment, they jeopardize the patient or require intervention to prevent one of the outcomes listed above.

The date that an AE meets 1 of the criteria listed above is the date that it becomes an SAE. Conversely, the date that the SAE no longer meets 1 of the criteria listed above is the end date of the SAE. A new AE with an outcome of “recovering” may be created to address the ongoing AE once it is no longer considered serious.

Serious adverse events will be assessed and recorded after the first administration of study drug and ending on Extension Day 561 (± 3) or 84 (± 3) days after last dose of study drug if ET.

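### Formal pregnancy capture ends 84 days after the last dose but contraception is required to 120 days, so for completers and early study terminators the protocol does not ask about pregnancies arising in days 85 to 120

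*Combined protocol and SAP*

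**What the plan says.** - **Capture.** Section 13.7.3 records pregnancies in female patients and in partners of male patients from first exposure "through Extension Day 561 (± 3) or 84 (± 3) days after last dose of study drug if ET". Section 5.1 and Table 1, note 23, show that ET here means leaving the study early, not only stopping drug.
- **Patient notification.** The same section says: "Male patients must be instructed to inform the Investigator immediately if their partner becomes pregnant during the study". Female patients get a parallel instruction with the same limit. Inclusion criterion 6 (7.3) tells men to make contact if they "suspect their partner might be pregnant at any time during study participation".
- **Contraception.** Inclusion criteria 5 and 6 require it "until the end of the study or for 120 days following the last dose of study drug, whichever is longer".
- **Undated duties.** Section 13.7.3 adds: "The Investigator must report any pregnancy to Allakos within 24 hours of becoming aware of it". Section 11.4.3 sets a similar 24-hour duty for pregnancies in treated patients. Neither has an end date.
- **SAEs.** Section 13.2 says: "Serious adverse events will be assessed and recorded after the first administration of study drug and ending on Extension Day 561" (or 84 days after the last dose if ET). Section 13.7.3 says without a date: "Any congenital abnormalities noted at birth in the offspring of a patient who received study drug will be reported as a SAE".
- **Half-life.** Exclusion criterion 4 (7.4) refers to "vaccination expected within 5 half-lives (4 months) of AK002 administration".

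**The concern.** The sponsor asks patients to avoid pregnancy for 120 days after the last dose, but stops formal capture of pregnancies at 84 days. In the days between, a pregnancy is something the protocol wants to prevent but does not ask to hear about.

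After the last visit, the site will usually learn of a pregnancy only if the patient says so. The last scheduled pregnancy test is 35 days after the last dose (11.4.3), and partners are not tested at all. The request to the patient is therefore the working part of the system.

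What is at stake is safety information on exposed pregnancies, which will be few, in a study whose stated objective includes longer-term safety. SAE handling is also unclear for a serious maternal complication of a pregnancy that begins after SAE recording has ended.

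**Working it through.** **Inputs.** Last scheduled dose: Day 477 ± 3 (9.4). Follow-up: 84 ± 3 days after the last dose (5.1). Completion: Day 561 ± 3 (14.1). Contraception: 120 days (7.3). Five half-lives: 4 months (7.4). Method effectiveness: 99%, 96% and 91% (11.4.4).

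**1. The plan's own dates.** Dose 18 falls on 1 + 17 × 28 = Day 477. Then 477 + 84 = Day 561, which reproduces the stated end of capture.

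**2. The gap for completers and early study terminators.** 477 + 120 = Day 597, and 597 − 561 = 36 days (days 85 to 120), or 36/120 = 30% of the contraception period. After early termination, 120 − 84 = 36 days as well.
- Both limits counted from the actual last dose, ± 3 on the 84 days: 120 − 87 = 33 to 120 − 81 = 39 days.
- Day 561 ± 3 read as a fixed extension day, with the Day 477 dose also varying by ± 3: (474 + 120) − 564 = 30 to (480 + 120) − 558 = 42 days.

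**3. Patients who stop drug early but stay on study to Day 561** (encouraged in 14.2). There is no gap if the last dose is on or before 561 − 120 = Day 441.
- Last dose Day 449: 449 + 120 = Day 569, a gap of about 8 days.
- Last dose Day 421: 421 + 120 = Day 541, before Day 561, so no gap. The same holds for every earlier scheduled dose.

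**4. Drug remaining.** This assumes first-order elimination and 4 months = 120 days, so a half-life of 120/5 = 24 days.
- Day 84: 84/24 = 3.5 half-lives; 2^−3.5 = 8.8% of the last-dose level.
- Day 120: 5 half-lives; 2^−5 = 3.1%.
- If the 4 months were rounded from anything between 3.5 and 4.5 months (an assumption), the Day 84 figure runs from about 6.5% to 12%.

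**5. Expected pregnancies in 36 days.** The documents do not give the number of patients or partners able to conceive, so 25 to 100 people are assumed. The effectiveness figures are read as yearly failure rates of 1%, 4% and 9%, also an assumption. Formula: people × yearly rate × 36/365.

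| People | 1% | 4% | 9% |
|---|---|---|---|
| 25 | 0.02 | 0.10 | 0.22 |
| 50 | 0.05 | 0.20 | 0.44 |
| 100 | 0.10 | 0.39 | 0.89 |

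An expected count of one needs 365/(36 × 0.09) = about 113 people, all at 9%, against a planned maximum of about 183 patients. If the gap were 30 or 42 days for all 100 people, the largest cell would be 100 × 0.09 × 30/365 = 0.74 or 100 × 0.09 × 42/365 = 1.04.

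The 9% column is not a safe upper bound. Men need only one highly effective method, and that category includes the 91% options. Section 11.4.4 also lets subjects who entered on dual methods without a highly effective one continue, and gives no failure rate for them. Women who use dual methods with a highly effective one, or abstain, should do better than the single-method rates.

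**The case against.** The strongest objection is that the protocol already handles the event itself. Any pregnancy the Investigator learns of must go to the sponsor within 24 hours, with no end date and with partners included. Pregnancies in treated patients are followed through term, and congenital abnormalities are SAEs whenever noted. A pregnancy that begins before capture closes is covered even if recognised later. The patient instruction may also appear in the consent form, which was not available for this review.

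Most of this stands, and it rules out several stronger readings that a reader might infer:
- **That late pregnancies would go unreported.** The undated duties in 11.4.3 and 13.7.3 say otherwise. What is missing is formal capture and the request to patients.
- **That 13.7.3 sets an explicit 84-day limit on patient notification.** It limits notification to the study; the 84 days is inferred from where follow-up and completion end.
- **That everyone has a 36-day gap.** Patients who stop drug early and stay on study do not.
- **That the 120 days was derived from the half-life.** The two lengths agree, but no section links them. The half-life figure stands in a vaccination criterion.
- **That birth defects fall outside SAE reporting after Day 561.** Section 13.7.3 covers them without a date.

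The objection does not close the remaining gap. The undated duties work only once the site knows, and no section of the protocol asks patients to report after the study ends.

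**Conclusion.** The point holds for completers and for patients who leave the study early: formal capture and the request to patients end about 36 days before the contraception requirement does (33 to 39 or 30 to 42 days, depending on how the visit windows are read). For patients who stop drug early but stay to Day 561, the gap is about 8 days after a last dose on Day 449, and none after a last scheduled dose on Day 421 or earlier.

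The consequence is small. The expected number of pregnancies is probably below one under the assumed 25 to 100 people at risk and failure rates of 1% to 9%. No efficacy result is affected. The mismatch in dates rests on the protocol text alone; the residual-drug and expected-count figures rest on the assumptions stated with them and only give a sense of scale. Severity is minor: a cheap improvement in safety capture.

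**What to change.** **In 13.7.3:**
1. End capture, for patients and partners, at the later of the end of the study and 120 days after the last dose (Day 597 for a completer dosed on Day 477). Taking the later date avoids shortening capture for patients who stop drug early and stay on study.
2. Extend the notification instruction for women and men to the same date.
3. Remind patients of it at the last visit they attend. After early termination that may be the Day 35 visit, which leaves 120 − 35 = 85 days to cover.
4. State that a serious complication of a pregnancy captured in this window is reported as an SAE even after Day 561. Congenital abnormalities need no new sentence.

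Leave the undated duties in 11.4.3 and 13.7.3 as they are. No visit or test is added, so capture still depends on the patient's report, but that report is now requested.

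**Cost.** A wording amendment with prior written IRB approval and each Investigator's signature (17.1), at approximately 60 centers, and possibly a consent form update. It could be combined with another amendment if one is made; the protocol does not mention one. The other downsides are a few late reports and a pregnancy end date that differs from the 84-day AE end date.

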13.7.4 Adverse Event of Special Interest Reporting

Beginning from the time of first study drug infusion and ending on Extension Day 561 (± 3) or 84 (± 3) days after last dose of study drug if ET, any new AESI (or new information related to a previously reported AESI) must be recorded in the Adverse Event eCRF and designated as an “adverse event of special interest.”

An AESI that also qualifies as a SAE (per Section 13.2) must also be reported as a SAE in accordance with Section 13.7.2. Adverse events of special interest that are also SAE must be recorded in the Adverse Event eCRF and designated as both “serious” and as an “adverse event of special interest.” These will be reported on the Sponsor-provided SAE forms and should be reported to the Sponsor within 24 hours of site awareness.

13.9 Study Withdrawal Criteria

Patients will be discontinued from the study in the event that:

- Occurrence of an exclusion criterion, which is clinically relevant and affects the patient's safety, if discontinuation is considered necessary by the Investigator and/or Sponsor.
- Serum transaminases (ALT and/or AST) $>3 \times$ upper limit of normal (ULN) **and** total bilirubin $>2 \times$ ULN (confirmed by subsequent repeat) without an alternative explanation.
- Elevation of ALT and/or AST $>3 \times$ ULN (confirmed by repeat) with the appearance or worsening of symptoms thought by the Investigator to be potentially related to hepatic inflammation such as fatigue, nausea, vomiting, right upper quadrant pain or tenderness, fever, and rash.

13.10 Study Stopping Rules

The study may be discontinued prematurely in the event of any of the following:

- A life-threatening AE that is possibly or probably related to treatment.
- A fatal AE that is possibly or probably related to treatment.
- New information leading to unfavorable risk-benefit judgment of the study drug.
- Sponsor's decision that continuation of the study is unjustifiable for medical or ethical reasons.
- Discontinuation of development of the Sponsor's study drug.
- Approval by Health Authorities of the Sponsor's study drug.

Health Authorities and IRB will be informed about the discontinuation of the study in accordance with applicable regulations. The study may be terminated or suspended on request of Health Authorities or Sponsor.

14. Discontinuation and Replacement of Patients

14.1 Definition of Study Completion

A patient who completes visits through Extension Day 561 (± 3) will be recorded as having completed the study.

14.2 Early Discontinuation of Study Drug

A patient may be discontinued from study treatment at any time if the patient, the Investigator, or the Sponsor feels that it is not in the patient's best interest to continue. The following is a list of possible reasons for study treatment discontinuation:

- Patient withdraws consent.
- An AE that in the opinion of the Investigator results in it being in the best interest of the patient to discontinue study treatment.
- Protocol violation requiring discontinuation of study treatment.
- Participation in any other study during the duration of this study.
- Use of a non-permitted concomitant drug without prior approval from the Medical Monitor.
- Loss of ability to freely provide consent through imprisonment or involuntary incarceration for treatment of either a psychiatric or physical (e.g., infectious disease) illness.

If a patient is withdrawn from treatment due to an AE, the patient will be followed and treated by the Investigator or designee until the abnormal parameter or symptom has resolved or stabilized.

All patients who discontinue study drug treatment should be encouraged to continue on study and complete assessments and procedures according to [Table 1](#), if possible.

Reasonable attempts will be made by the Investigator to provide reasons for patient withdrawals. The reason for the patient's withdrawal from the study or all attempts to acquire such, will be specified in the source documents.

15. Statistical Methods and General Considerations

This section outlines the nature and rationale for the statistical methods to be used for analysis of the data from the study. A separate Statistical Analysis Plan will describe data handling and statistical techniques in full detail. The Statistical Analysis Plan will contain any modifications to the analysis plan described below.

All patient data will be listed. When appropriate, summary statistics of number of non-missing values, mean, median, standard deviation, minimum, and maximum will be computed for continuous variables, and summary statistics of number and percentage will be computed for categorical variables. No formal statistical inferences will be made. No imputation will be used for missing data.

